## 4. B. Study Procedure

Study will begin before patient's discharge from the hospital and last for 194 days.

Baseline: Will occur during the duration of admission stay in the hospital. Patients will have a medical history taken as well as smoking history. Patients will also be given a physical exam including vital signs. A spirometry test will also be performed. Women with the potential to become pregnant will be given a pregnancy test. Data will also be collected in regards to dyspnea scales, Deyo-Charlson index, and GOLD classification. Patients will complete a Columbia Suicide Severity Rating Scale to exclude patients with a history of suicidal behavior  $\leq 2$  years or suicidal ideation  $\leq 6$  months prior to enrollment Randomization: Patients who are eligible to enroll in this study will be randomized to one of two treatment groups. Randomization will be done using a randomized block design stratified by treatment center. One group will receive rollumilast 500 mcg (Daliresp®) and the other will receive a placebo tablet. Patients will begin one of these treatment arms prior to hospital discharge for a total period of 180 days post enrollment.

Day of hospital discharge: A spirometry test will be performed and an adverse event assessment will be completed.

Day 7: Phone Visit. Data to be collected includes: interim history, adverse events assessments, vital status, and exacerbation history. During this telephone visit the study doctor or nurse coordinator will ask how the patient is feeling and if they have needed to visit the doctor or go to the emergency room or hospital since the last time they were contacted. They will be asked how well they are tolerating the study drug.

Day 14: Clinic Visit. At this visit vital signs, C-SSRS test, interim history, adverse event assessment, vital status, and exacerbation history will be recorded. The following questionnaires will given: EQ-5D, the St. George's Respiratory Questionnaire (SGRQ), and the Modified Medical Research Council dyspnea score (MMRC).

Days 30, 60, 90, & 120: Phone Visit. Data to be collected includes: interim history, adverse events assessments, vital status, and exacerbation history. During each of these telephone visits the study doctor or nurse coordinator will ask how the patient is feeling and if they have needed to visit the doctor or go to the emergency room or hospital since the last time they were contacted. They will be asked how well they are tolerating the study drug.

Day 180: Clinic Visit. At this visit vital signs, C-SSRS test, interim history, adverse event assessment, vital status, and exacerbation history will be recorded. A spirometry test will be performed as well during this visit. The following questionnaires will given: EQ-5D, the St. George's Respiratory Questionnaire (SGRQ), and the Modified Medical Research Council dyspnea score (MMRC).

Day 194: Phone Visit. This phone call covers the wash out period for the study treatments. Data to be collected includes: interim history, adverse events assessments, vital status, and exacerbation history. During this telephone visits the study doctor or nurse coordinator will ask how the patient is feeling and if they have needed to visit the doctor or go to the emergency room or hospital since the last time they were contacted.

**4. C. Demographics and Medical History**. Age, gender, body mass index (BMI), smoking history (debut, amount, duration), presence of comorbidities, current medical therapy (bronchodilators, steroids, oxygen), history of pulmonary rehabilitation, influenza and pneumococcal vaccination, emergency room visits and hospitalizations during last year, number of prior exacerbations in prior year, history of coronary artery disease, stroke, transient ischemic attacks, and peripheral vascular disease. The Deyo-Charlson index, a standard and validated measure of co-morbidity {{252 Deyo,R.A. 1992; }}, will be used to assess the impact of other chronic illnesses on outcome.

**4. D. Spirometry.** Spirometry will be performed (post bronchodilator administration) at enrollment (baseline) or as soon as the subject is able to perform it after hospitalization, at the day of discharge and then 180 days post randomization according to ATS guidelines. {{174 Anonymous American Thoracic Society. 1995}} We realize that all subjects may not be able to perform spirometry initially upon presentation, but Niewoehner has reported that spirometry was able to be performed in a multicenter trial in acute hospitalized COPD patients 96% of the time at some point during the initial hospitalization.{{1143 Niewoehner,D.E. 2000}}Data will be presented in absolute numbers and as percent of reference predicted values, using prediction equations from Crapo {{233 Crapo,R.O. 1981}} for whites and by multiplying Crapo's predicted values by 0.88 to correct for blacks' smaller lung volumes. Airflow obstruction will be defined by postbronchodilator measured FEV1/FVC < 70% and FEV1 < 70% predicted at time of inclusion and will be used to define GOLD Grades.{{154 Global Initiative for Chronic Obstructive Lung Disease (GOLD) Guidelines.}}

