## Outcomes:

In this pilot proposal, 100 patients at three centers will be evaluated to test the feasibility of conducting this study and to assess the treatment effect of roflumilast to be able to power an appropriate definitive phase III multicenter trial. Our ultimate aims of the phase III trial will be:

**1) Primary**: time to all-cause mortality or re-hospitalization during the 180 days postrandomization. **2) Secondary:** respiratory death or respiratory re-hospitalization during the 180 days post-randomization; rate of death or readmission during the 30 days postdischarge; treatment failure (see definition below); change in health status, FEV1, and dyspnea during the 180 days post-randomization; length of hospital stay during the index hospitalization. **3) Other: assess tolerance of roflumilast vs. placebo in hospitalized AECOPD.** 

[figure not shown]

Figure 4 shows the overall study design, proposed study measurements, and time points for assessment. Patients hospitalized with AECOPD will be eligible for enrollment during their hospitalization with treatment being started before discharge from the hospital.. Demographics, blood tests, health related quality of life, comorbidity (Deyo-Charlson index), post bronchodilator spirometry, vital signs, dyspnea measured by MMRC, SaO2 and amount of inspired O2 to maintain SaO2> 90% at rest, serum fibrinogen levels, HBA1c, Biomarkers and Genetics will be obtained after enrollment and then patients will be randomized to standard AECOPD care plus roflumilast 500 ug daily vs. placebo. Patients will begin roflumilast or placebo  $\leq$  12 hours of hospitalization for a total period of 180 days post enrollment. On discharge day (approximately day 3-4 after admission based on the recent COPD CRN zileuton study of hospitalized AECOPD), the measurements will be repeated as indicated (baseline measurements), with follow-up phone assessments at days 7, 30, 60, 90, 120 and 194 days post enrollment. An inperson clinical visit will be conducted at days 14 and 180 post randomization.

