prospectively assesses suicidal ideation and behavior using a structured interview face to face for patient responses. The C-SSRS will be performed during each evaluation visit according to the assessment schedule on Figure 4. Suicidal ideation is classified on a 5-item scale: 1 (wish to be dead), 2 (nonspecific active suicidal thoughts), 3 (active suicidal ideation with any methods [not plan] without intent to act), 4 (active suicidal ideation with some intent to act, without specific plan), and 5 (active suicidal ideation with specific plan and intent). The C-SSRS also captures information about the intensity of ideation, specifically the frequency, duration, controllability, deterrents, and reasons for the most severe types of ideation. Suicidal behavior is classified on a 5-item scale: 0 (no suicidal behavior), 1 (preparatory acts or behavior), 2 (aborted attempt), 3 (interrupted attempt), and 4 (actual attempt). The C-SSRS will be performed during each evaluation visit according to the assessment schedule (see Figure 4). During visit, patients will complete the assessment with the health professional. Patients who do not have suicidal behavior or ideation will answer a limited number of questions and will usually complete the assessment in approximately 3 minutes. Patients with significant suicidal ideation and/or behavior may require up to 10 minutes to answer all relevant questions.

The patient should not be released from the evaluation site until it is confirmed

that the patient is not considered to be at any suicidal risk and all responses negative to the C-SSRS.

Positive reports are generated for any of the following findings:

- Suicidal ideation with intention to act (score of "4")
- Suicidal ideation with specific plan and intent (score of "5")
- Made suicide attempt
- Interrupted suicide attempt
- Aborted suicide attempt
- Preparatory behaviors for making a suicide attempt

At Screening (Visit 1), the C-SSRS will be completed for the patient's lifetime history

of suicidal ideation and behavior. At all other visits, the C-SSRS will be completed for Version 04.13.2015

ideation and behavior since the previous visit. The patient's responses should remain negative throughout the entire trial. If a possible exclusion alert is triggered

by a positive response at Screening (Visit 1), 2 additional questions at the bottom of the

report will need to be asked to determine whether exclusion criteria 9a and/or 9b have

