## 4. N. Contraindications and side effects to the use of Roflumilast.

**1. Contraindications**: Roflumilast in contraindicated in patients with moderate or severe liver impairment (Child-Pugh class B and C)

2. Side effects: Adverse events experienced by > 3% of patients in clinical trials of roflumilast included diarrhea (9.5%), weight loss (7.5%), nausea (4.7%), headache (4.4%) and back pain (3.2%). Patients discontinued therapy due to adverse effects more frequently with roflumilast (14.8%) compared to placebo (9.9%). Diarrhea and nausea were the most common adverse reactions leading to drug discontinuation in prior trials. Serious adverse events that occurred more frequently with roflumilast compared to placebo included diarrhea, atrial fibrillation, lung cancer, prostate cancer, acute pancreatitis acute renal failure. Less common adverse events, (1-2%) of patients that were more frequently reported with roflumilast use as compared to placebo included abdominal pain, anxiety, heartburn, depression, gastritis, rhinitis, sinusitis, muscle spasms, tremor, urinary tract infection, and vomiting. Roflumilast carries a warning for increased psychiatric adverse events and suicidality. Patient should be monitored for changes in mood including worsening insomnia, anxiety or depression or suicidal ideations. Roflumilast also carries a warning for weight loss. 20% of patients may experience moderate weight loss between 5 to 10% of ideal body weight compared to 7% with placebo.

Roflumilast side effects reported in  $\ge 2\%$  of recipients from 8 clinical trials as listed in the manufacturer's package insert are listed in the table below.

Treated with Roflumilast 500 mcg daily and Greater Than Placebo Treatment		
Adverse Reactions	Roflumilast	Placebo
(Preferred Term)	(N=4438)	(N=4192)
	n (%)	n (%)
Diarrhea	420 (9.5)	113 (2.7)
Weight decreased	331 (7.5)	89 (2.1)
Nausea	209 (4.7)	60 (1.4)
Headache	195 (4.4)	87 (2.1)
Back pain	142 (3.2)	92 (2.2)
Influenza	124 (2.8)	112 (2.7)
Insomnia	105 (2.4)	41 (1.0)
Dizziness	92 (2.1)	45 (1.1)

Decreased appetite	91 (2.1)	15 (0.4)

Other side effects reported in 1- 2% of recipients include: Gastrointestinal disorders (abdominal pain, dyspepsia, gastritis, vomiting); Infections and infestations (rhinitis, sinusitis, urinary tract infection); Musculoskeletal and connective tissue disorders (muscle spasms); Nervous system disorders (tremor); and Psychiatric disorders (anxiety, depression).

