been met. A response of "Yes" to either one or both of the follow-up questions will exclude the patient from the trial and necessitate immediate psychiatric referral of the patient on the same date as the screening visit. For all subsequent visits after Screening (Visit 1), if the patient's response generates a change in the findings report from negative to positive, the patient should be referred for immediate psychiatric evaluation on the same date as the site visit and the PI will should be contacted. Positive suicidality indication findings reports after the Screening Visit (Visit 1), if confirmed by the *Investigator*, should be considered to be an AE. Ultimately, the determination of suicidality and risk is up to the *Investigator*'s clinical judgment.

Columbia – Suicide Severity Rating Scale Process

Forms:

Baseline/Screening Version

Since Last Visit Version

- Screening/Baseline Visit: Patient must not have a history of suicidal behavior ≤ 2 years or suicidal ideation ≤ 6 months prior to enrollment. The Screening/Baseline Version will be used to screen patients. During screening, if there is a positive response to questions 1 thru 5 do not enroll patient and notify the PI for possible psychiatric referral.
- 2. Clinic Visit 14 or Clinic Visit 180
  - During study patient's follow up clinic visit, the coordinator will assess for suicide risk utilizing the Since Last Visit version. A positive answer to question 4 or 5 indicating presence of ideation with at least some intent to die suggests a clear need for further evaluation or clinical management. Discuss with PI while patient still at visit C-SSRS score. Patient's scoring a 4 or a 5 should be discontinued from study and sent to Temple ER or to Episcopal ER for immediate evaluation.

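### After entry, suicidality is scheduled for assessment only at days 14 and 180, and the calls in between do not prompt for mood, insomnia or ideation

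*Combined protocol and SAP*

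**What the plan says.** Section 4.N reports that the drug carries a warning for psychiatric events and suicidality, and adds: "Patient should be monitored for changes in mood including worsening insomnia, anxiety or depression or suicidal ideations". It gives no instrument or timetable for this.

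Section 4.H describes the C-SSRS as a face-to-face structured interview, done at every evaluation visit on the schedule in Figure 4. After screening it works by recall: "At all other visits, the C-SSRS will be completed for" ideation and behavior since the preceding visit.

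The visit text is narrower. At entry the scale serves as a screen (section 4.B: "Patients will complete a Columbia Suicide Severity Rating Scale to exclude patients with a history of suicidal behavior"). After entry, section 4.B lists it at day 14 and day 180 only. The appendix puts the follow-up form under "Clinic Visit 14 or Clinic Visit 180". These are the only in-person follow-up visits (section 3.B, Outcomes: "An inperson clinical visit will be conducted at days 14 and 180 post randomization").

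The remaining contacts are telephone calls: "follow-up phone assessments at days 7, 30, 60, 90, 120 and 194 days post enrollment". For those at days 30, 60, 90 and 120, section 4.B says "Data to be collected includes: interim history, adverse events assessments, vital status, and exacerbation history". The caller also asks how the patient feels, whether care was sought and how the drug is tolerated. The C-SSRS is not listed for any call, including day 7 and the washout call at day 194.

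On treatment length, section 4.B says: "Patients will begin one of these treatment arms prior to hospital discharge for a total period of 180 days post enrollment".

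**The concern.** The protocol takes this risk seriously: it has a stated warning, an exclusion criterion, a dedicated instrument and a management table. Yet after day 14 no contact before day 180 is scheduled to ask about it directly.

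Three things are at stake.

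- **Detection during treatment.** The appendix procedure for a follow-up score of 4 or 5 is written for the day-14 and day-180 visits. During the treatment period it can therefore act only from day 14. By day 180 planned treatment is ending.
- **Data for the tolerance aim.** Tolerance is the first specific aim in section 4.Q. For suicidality, more than five months rest on a single recall at day 180. Patients who die, withdraw or miss that visit contribute no C-SSRS after day 14.
- **Consistency.** Section 4.B labels its calls as visits. Read literally, the section 4.H rule would put the C-SSRS on every call, but the visit lists leave it out. Sites could follow either reading.

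**Working it through.** The documents state no figure for this interval, so there is none to reproduce. The check is date arithmetic on the schedule in section 3.B (Outcomes) and section 4.B.

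**Step 1. Lay out the scheduled contacts.** The discharge-day contact is left out because its date varies; section 4.B lists no C-SSRS there.

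| Contact | Days since previous | C-SSRS listed in 4.B |
|---|---|---|
| Entry | – | yes (screen) |
| Day 7 call | 7 | no |
| Day 14 clinic | 7 | yes |
| Day 30 call | 16 | no |
| Day 60 call | 30 | no |
| Day 90 call | 30 | no |
| Day 120 call | 30 | no |
| Day 180 clinic | 60 | yes |
| Day 194 call | 14 | no |

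**Step 2. Interval between the two follow-up assessments.** 180 − 14 = 166 days, and 166/180 = 92.2% of the treatment period. One C-SSRS (day 14) falls after entry and before the end of treatment. Four general adverse event calls fall inside the interval.

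**Step 3. Longest interval with no scheduled contact.** 180 − 120 = 60 days, and 60/180 = 33.3%. The three preceding intervals are 30 days each.

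**Step 4. Where day 180 falls.** Treatment runs 180 days from enrollment (section 4.B), while the clinic visit is counted from randomization (section 3.B, Outcomes). If the two dates coincide, the second assessment is at the end of planned treatment. The text does not say whether the last dose comes before or after the visit.

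**Step 5. Early stoppers.** Section 4.N cites stopping for adverse effects in 14.8% on roflumilast and 9.9% on placebo in prior trials. Assume equal arms of 50 and, for illustration only, the same rates here. Then 50 × 0.148 = 7.4 and 50 × 0.099 = 4.95 patients would stop early. If they are still followed, as section 4.P provides, their day-180 C-SSRS may come well after their last dose. The documents do not allow an estimate of how many patients would have no day-180 assessment.

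**The case against.** The strongest defence is that the trial does monitor. Four calls fall in the interval, each with an adverse event assessment and a tolerance question. Section 4.P defines adverse events broadly, and section 4.N already lists insomnia, anxiety and depression as known reactions. The scale is given at every in-person follow-up visit, and its recall wording covers the whole period. The sentence in section 4.N sets no frequency, so two assessments need not breach it. Figure 4 might show more.

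Much of this stands, and it rules out several stronger readings that a reader might infer:

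- *That 166 days pass with no assessment.* What is missing is a scheduled suicidality assessment; general adverse event review continues.
- *That a third of the treatment period goes unobserved.* The 60 days are a gap between contacts. The day-180 visit takes an interim history and adverse events for them.
- *That dosing is complete before the last assessment.* The text does not establish this (step 4).
- *That the protocol breaks its own monitoring instruction.* The instruction has no timetable to break.
- *That suicidality is the risk the protocol ranks highest.* Section 4.N ranks none, and lists other serious events.

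The defence does not supply a prompt. The calls can record a psychiatric event that the patient volunteers, but nothing in the listed content asks for one. Recall at day 180 can document an episode, but cannot detect it while treatment is under way. On Figure 4, the visit text and the appendix agree with each other; if the figure adds assessments, it conflicts with both and still needs reconciling.

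**Conclusion.** The point holds as a gap in scheduled, prompted assessment. In the visit text and appendix, 166 of 180 treatment days (92%) lie between two suicidality assessments. The four intervening calls have no mood, insomnia or ideation prompt, and the last 60 days before day 180 have no scheduled contact. The interval is covered by recall alone, and not at all by C-SSRS in patients who do not reach day 180.

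This should be changed because it bears on patient safety and on the tolerance aim, and the remedy is cheap. It does not invalidate the design or the primary analysis.

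The conclusion assumes that enrollment and randomization fall on or near the same day, and that the visit lists in section 4.B are what sites will follow. It is also conditional on Figure 4, which was not available.

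**What to change.** 1. Reconcile section 4.H (scale at every evaluation visit), section 4.N (monitoring for mood and ideation), the call content in section 4.B, the appendix and Figure 4, so that they give one schedule. State whether telephone calls count as visits for the C-SSRS.
2. Add a prompted mood, insomnia and suicidality item to the calls already scheduled. The Since Last Visit questions are one option.
3. In section 4.R, report positive answers by arm over all contacts, with the number of patients assessed at each.

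**Effect.** With prompts at days 30, 60, 90 and 120, the longest interval between prompted assessments during treatment falls from 166 to 60 days. The number after entry and before day 180 rises from one to five. The 60-day interval after day 120 remains, and the sponsor should say whether it is intended.

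**Cost.** Section 4.H puts the interview at about 3 minutes without ideation and up to 10 minutes with significant ideation or behavior. Calls at days 30, 60, 90, 120 and 194 add 5 × 3 = 15 minutes per patient, or 6 × 3 = 18 if day 7 is included. For 100 patients that is 100 × 15 = 1,500 to 100 × 18 = 1,800 minutes, or 25 to 30 hours of coordinator time.

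**Downside.** A telephone interview departs from the face-to-face description. Three provisions also presuppose that the patient is on site: holding the patient there until risk is excluded, referral on the date of the site visit (both section 4.H), and discussion with the investigator before the patient leaves (appendix). The sponsor must reconcile these with telephone contact. No referral or discontinuation rule is proposed here.

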## 4. E. Measurement of Hospitalization Duration.

Hospitalization duration will be measured both as the actual days of hospitalization, and as the number of days from admission to the day when patients meet criteria for discharge as outlined by others {{1028 Stevenson,N.J. 2005;415 Pinto-Plata,V.M. 2007; 90 Global Initiative for Chronic Obstructive Lung Disease (GOLD) 2008;}}. These criteria include: 1) stable vital signs (respiratory rate < 25 breath/minute, heart rate below 100 beats/minute, oral body temperature between 97 to 100°F) 2) ability to walk 50 feet without disabling dyspnea; 3) SpO2> 90% with  $\leq$  4 LPM oxygen at rest; 4) use of  $\beta$ -agonist therapy > every 4 hours; 5) no escalation of care within the previous 12 to 24 hours. We plan to use these criteria to define when patients can be discharged to calculate hospital duration rather than the number of hospitalization days to avoid the social and non-clinical obstacles that are inadvertently wrapped into length of stay (e.g., getting a ride home, too late in the day, need other support services, etc.).

